4.8 Trial assessments

Written informed consent is given by the patient in the first screening visit, which takes place before or shortly after surgery (allowing for randomization to be performed within 12 weeks from surgery).

In the second screening visit, which takes place after surgery, inclusion and exclusion criteria are assessed in patients with tumors harboring somatic alterations in the PIK3CA, PIK3R1 or PTEN genes. Patients without such somatic alterations, and patients not fulfilling all inclusion criteria, or fulfilling at least one exclusion criteria are excluded from the trial. However, patients with regular use of ASA (>3 doses/week) fulfilling all other eligibility criteria, are included in an observational arm.

Randomization takes place in the third visit, in which the subject is also provided with IMP for 200 days. The treatment period begins at the randomization visit and ends after 3 years.

A phone contact is made with the subject three months from randomization, and thereafter every sixth month. Also, subjects visit their respective site every sixth month from randomization, i.e,. the subjects are in contact with the site every third months for three years. At the end of the follow-up period, five years from randomization, there is an additional visit or phone contact for subjects who have completed three years in the trial (up to and including Visit 15). The trial assessments, starting from randomization, are visualized in Figure 2, and described in detail in Table 4.

[figure not shown]

Figure 2. Time-line of trial assessments. The dice icon refers to Randomization, the phone icon to Phone contact, the human icon to Clinic visit, and the skeleton icon to clinic visit including examination with CT/MRI.

Table 4. Overview of trial assessments

Assessment/Visit	Random- ization (R)	First phone call	First site visit	Subsequent phone calls	Subsequent site visits	Final visit/phone call
Visit no.*	3	4	5	6, 8, 10, 12, 14	5, 7, 9, 11, 13, 15	16
Timepoint	0	3mo after R	6mo after R	Every 6mo after first phone call	Every 6mo after first site visit	5y from R
Visit/call window	-	±21 days	±21 days	±21 days	±21 days	±30 days
Provide with IMP	Yes		Yes		Yes	
Assess AEs		Yes	Yes	Yes	Yes	
Subject asked about compliance		Yes	Yes	Yes	Yes	
Remaining pill count			Yes		Yes	
Record concomitant medication		Yes	Yes	Yes	Yes	
CT/MRI of thorax and abdomen					Yes (visit 7 and 15 – 1y and 3y after R)**	
Measure carcinoembryonic antigen (CEA)					Optional, visit 7 and 15 – 1y and 3y after R	Optional
Subject asked about regular use of ASA after end of trial intervention						Yes
CRC recurrence/Death (and corresponding dates)						Yes

^{*}Visits 1 and 2 are screening visits.

Subjects leave the IMP part of the trial at Visit 15, or at fulfillment of an end of study (EoS) reason. EoS reasons are

- Death,
- CRC recurrence,
- Severe unexpected AE,
- Pregnancy,

^{**}Two Finnish sites do not include CT/MRI of thorax and abdomen as part of their standard of care.

- Other medical reason (including other cancer),
- · Wanting to leave the study,
- · Lack of compliance with study protocol,
- Refusal to cooperate,
- Other reason (specified in the eCRF by study personnel).

4.8.1 Trial assessments during the COVID-19 pandemic

From April 4th, 2020, most clinic visits are switched to phone contacts, and subjects are provided with IMP by mail. Subjects are asked about their compliance at each phone contact, and remaining pills are counted whenever the subject has a possibility to visit the clinic. Remaining pill count is then retrospectively entered into the eCRF for each clinic visit that has been replaced with a phone contact. Study personnel have been encouraged to go back to clinic visits as the COVID-19 spread has decreased.

4.8.2 Treatment compliance

Every sixth month, subjects are provided with two boxes of IMP, each containing 100 pills. Subjects are to take one pill per day. Subjects treated with adjuvant chemotherapy, who, for medical reasons, should not receive ASA during said treatment are allowed to start taking the IMP after termination of chemotherapy. Subjects are also allowed to pause taking the IMP for up to 30 days in a row during the trial. All treatment pauses, for any reason, are entered with a start and end date in the eCRF.

At each phone contact and clinic visit, the subject is asked how often they forget to take the IMP, with response options

- Never/Rarely
- Once in a while
- Sometimes
- Often
- Always.

At each clinic visit, the subject brings the IMP packages provided to them at the preceding clinic visit, the remaining pills are counted mechanically and the sum is entered into the eCRF.

Compliance until the last clinic visit (C_{LCV}) will be calculated as

$$C_{LCV}$$
 % = $\frac{DP \text{ before the final clinic visit - RP up to and including the final clinic visit}}{TD until the final clinic visit - number of days on allowed break before the final clinic visit} •100,$

where DP refers to the total number of dispensed pills, RP to the total number of remaining pills, and TD to the total number of potential treatment days. The number of days on break before the final clinic visit only includes breaks that are maximum 30 days or related to adjuvant chemotherapy, i.e. breaks that are allowed by the study protocol.

Subjects with an EoS event before the first clinic visit, in which the first pill count takes place, but after the first phone contact, will not have any pill counts in the eCRF. However, they will have been asked at the first phone contact (Visit 4) how often they forget to take the IMP. Compliance until Visit 4 (C_{V4}) for these subjects will be defined as 80 % if the response is "Never/Rarely" or "Once in a while", and 0 % if the response is "Sometimes", "Often", or "Always". C_{LCV} (or C_{V4}) for subjects with visits outside of the allowed time-window of ± 21 days will be calculated similarly as if their visits had been within the allowed time-window.

Subjects leaving the trial for any reason between two clinic visits, or between the first phone contact and the succeeding clinic visit, will not have a compliance measurement for the time between the last clinic visit (or Visit 4) and trial exit. For these subjects, an assumption on how long C_{LCV} (or C_{V4}) is assumed valid must be made. Denote the last date for which C_{LCV} (or C_{V4}) is assumed valid $D_{LCV/V4}$. For subjects experiencing recurrence, death, or other cancer, $D_{LCV/V4}$ will be defined as the date of last IMP intake, if such a date is registered in the eCRF, or the event date (see Section 6.2.1 for definition), whichever comes first. For subjects leaving the trial before an endpoint or before trial completion, $D_{LCV/V4}$ will be defined as the date of last IMP intake, if such a date is registered in the eCRF, or the Visit 15 date/EoS date, whichever comes first. For subjects completing 3 years in the trial, $D_{LCV/V4}$ will be defined as the date of Visit 15 (the 3-year follow-up clinic visit). The number of days for which C_{LCV} (or C_{V4}) will be assumed valid will be calculated as days from randomization until $D_{LCV/V4}$, subtracting the number of days on treatment breaks (before $D_{LCV/V4}$) not allowed by the protocol (see above), for each randomized subject having received the IMP at least once.

For subjects reaching a trial endpoint, days from $D_{LCV/V4}$ until the event date will be defined as having 0 % compliance. Similarly, for subjects leaving the trial before completion, days from $D_{LCV/V4}$ until 3 years from randomization will be defined as having 0 % compliance. For all subjects, regardless of trial completion or exit, days on treatment breaks (before $D_{LCV/V4}$) not allowed by the study protocol will be defined as having 0 % compliance. Overall compliance (OC) will be calculated as a weighted average between C_{LCV} (or C_{V4}) and 0, as follows

OC % =
$$\frac{\text{Valid days*C}_{\text{LCV or V4}} + \text{Zero-compliance days*0}}{\text{Valid days+Zero-compliance days}}.$$

Subjects with an EoS event before the first phone contact will not have answered the question on frequency in taking the IMP, or have any pill counts in the eCRF, hence, it is not possible to calculate compliance for such subjects.

See 6.2.2 for derivation of the variables needed for compliance calculation.

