6.2.2 Variables for compliance calculation

See Section 4.8.2 for the definition of overall compliance.

The number of treatment days until the last clinic visit will be calculated as days from the date of randomization (*A_randomiseringsdatum*) until the date of the last clinic visit (*V_Visitdatum* for the latest clinic visit, where clinic visits are *V_Visit* V5, V6, V7, V8, V9, V10, V11, V13, V15).

The number of dispensed pills at a certain clinic visit will be calculated as 100 times the number of unique package numbers (*S_Package_Number*) for packages that are not shredded (*R2465T32612_MAKULERAD*) or not found at the clinic (*S_Not_Found*).

The total number of dispensed pills will be calculated as the sum of the dispensed pills at each visit.

The total number of remaining pills will be calculated as the sum of the number of remaining pills for each clinic visit (S_returned_number). If the package was lost by the subject (S_Lost_Drug="True"), and S_returned_number equals 0 or "NA", the number of remaining pills for that package will be defined as 100, to not overestimate compliance.

The number of days on break will be calculated as the sum of days from $V_UppehallFromDatum$ until $V_UppehallTomDatum$, for all visits where $V_Uppehall=1$. Treatment breaks that are longer than 30 days and unrelated to adjuvant chemotherapy will be defined as non-compliant with the study protocol. Similarly, breaks that are at most 30 days of related to chemotherapy will be defined as compliant with the study protocol. Days on treatment break that are overlapping with a later registered treatment break will be subtracted.

Compliance for subjects with an EoS event after the first phone contact but before the first clinic visit will be based on the variable *V_LMIntag* for *V_Visit*=V4.

The date for which C_{LCV} (or C_{V4}) is considered valid until ($D_{LCV/V4}$) is $E_sistaintag$, dfs_event_date , $E_endofstudydtm$, or $v15_visitdatum$. The number of valid days will be calculated as the number of days from randomization ($A_randomiseringsdatum$) until $D_{LCV/V4}$, subtracting the number of days on non-allowed treatment break (see above). The number of zero-compliance days will be calculated as days from $D_{LCV/V4}$ until $E_endofstudydtm$ or 3 years from randomization, adding the number of days on non-allowed treatment break.

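### Pill-count compliance has no upper limit in the SAP, so unreturned surplus tablets can offset days scored as zero and lift a subject over the 80% per-protocol threshold

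*SAP*

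**What the plan says.** Supply and intake are fixed in SAP 4.8.2: "Every sixth month, subjects are provided with two boxes of IMP, each containing 100 pills", and "Subjects are to take one pill per day". SAP 4.8 gives the same amount in days: at randomization "the subject is also provided with IMP for 200 days".

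C_LCV is (DP − RP) divided by (TD − allowed break days), times 100. Here "DP refers to the total number of dispensed pills, RP to the total number of remaining pills", and TD is the number of potential treatment days. On breaks, "The number of days on break before the final clinic visit only includes breaks that are maximum 30 days or related to adjuvant chemotherapy".

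The next step is in the same section: "Overall compliance (OC) will be calculated as a weighted average between" C_LCV and 0, with valid days and zero-compliance days as the weights. For endpoint subjects, the days from the last date on which C_LCV is taken as valid (the last recorded intake, if there is one) "until the event date will be defined as having 0 % compliance".

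SAP 5.2.2 requires at least 80% compliance for PP3 and PP5. The one guard against overstatement is in SAP 6.2.2: a package flagged as lost, with a returned number of 0 or missing, is counted as 100 tablets remaining, "to not overestimate compliance". No sentence in 4.8.2 or 6.2.2 truncates C_LCV or overall compliance.

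**The concern.** At one tablet a day, compliance cannot exceed 100%. The formula can, because the supply exceeds the days it covers and every tablet not returned is treated as taken. Tablets thrown away, kept at home or taken in excess all raise the score.

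A value above 100% would do no harm if it stood alone against the 80% threshold. It matters because overall compliance is a product: the excess over 100% is spread over the valid days and pays for days that the SAP itself scores as zero. A subject below 80% on the SAP's own zero-day rule can then be kept in PP3 or PP5. The lost-package rule shows that the authors meant to avoid this kind of error, but it does not reach loose tablets. At stake is whether the 80% criterion applied is the one stated.

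**Working it through.** **Inputs.** 200 tablets per supply, one a day, threshold 80% (SAP 4.8, 4.8.2, 5.2.2). Six months = 365.25/2 = 182.6 days.

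**The plan's own figure.** 2 × 100 tablets at one a day = 200 days, which agrees with SAP 4.8. The surplus is 200 − 182.6 = 17.4 tablets per interval.

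**Largest C_LCV at nominal spacing, nothing returned.** 200/182.6 = 109.5% (200/183 = 109.3%). Over six supplies it is the same: 1200/1095.75 = 109.5%.

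**Largest share of zero-compliance days that passes.** Let f be that share. OC = (1 − f) × C_LCV ≥ 80% gives f ≤ 1 − 0.80/C_LCV.

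- Uncapped, C_LCV = 109.5%: f ≤ 26.95%, about 27%.
- Capped at 100%: f ≤ 20.0%.

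**Dependence on returns (uncapped).**

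| Tablets returned per interval | C_LCV | Largest f |
|---|---|---|
| 0 | 109.5% | 26.95% |
| 5 | 106.8% | 25.1% |
| 10 | 104.0% | 23.1% |
| 17.4 (exact one-a-day use) | 100.0% | 20.0% |

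Protocol 10.7.3 describes the supply as six months plus one week. Taking that as 190 tablets (an assumption), C_LCV is at most 104.0% and f at most 23.1%.

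**Routes above 109%, nothing returned.** First clinic visit at day 162 (21 days early): 200/162 = 123%, f ≤ 35%. One allowed 30-day break within a single interval: 200/152.6 = 131%, f ≤ 39%.

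**Worked case.** Visit 5 on day 183 with nothing returned, last intake on day 220, recurrence on day 300. Visit 7 is due at month 12, so no pill count intervenes.

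- As written: OC = 109.3% × 220/300 = 80.1%, in PP3.
- Truncated: OC = 100% × 220/300 = 73.3%, out.

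**When the cap can matter for endpoint subjects.** Suppose the last clinic visit is at month 6k, the subject stops after it, and the event comes before month 6(k + 1). The off-drug share is then at most 1/(k + 1).

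| Event in months | Largest off-drug share | Largest share that passes uncapped | Capped |
|---|---|---|---|
| 6–12 | 50% | 27% | 20% |
| 12–18 | 33% | 27% | 20% |
| 18–24 | 25% | 25% | 20% |
| 24–30 | 20% | 20% | 20% |
| 30–36 | 16.7% | 16.7% | 16.7% |

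From month 24 the cap changes nothing on this route. Subjects assessed at Visit 4 only get 80% or 0% and are not affected.

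**Non-allowed breaks before the last clinic visit.** These days stay in TD and are also scored as zero, so they count twice. If the break tablets are returned and intake is otherwise one a day, OC = (1 − f)², so f ≤ 1 − √0.80 = 10.6%. If the surplus from the on-drug time is not returned, f ≤ 1 − √(0.80/1.095) = 14.5%. Both limits are stricter than 20%.

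**The case against.** The case for leaving the formula alone is mostly about reach, and much of it stands.

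- A cap still lets 20% zero-compliance days through. The missing cap adds about 7 percentage points at nominal spacing, and only if all of about 17 surplus tablets per interval go unreturned. A subject who takes one a day and returns the rest scores exactly 100%.
- Remaining tablets are counted at each clinic visit, protocol 10.7.4 requires discrepancies between dispensed and returned product to be explained, and packages recorded as lost count as 100 remaining. The documents give no figure suggesting that non-return is common.
- SAP 5.2.2 already excludes subjects who leave because of an adverse event, other medical reasons, their own wish, non-compliance or refusal.
- PP3 and PP5 analyses are exploratory in the SAP (8.3) and carry no p-values.

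These points limit the size of the problem without removing it. Accountability records do not enter the formula, and the lost-package rule needs a package flagged as lost. The worked case needs only one supply with nothing returned and a stop between clinic visits. SAP 4.8.1 adds that from April 2020 drug was mailed and counts were entered retrospectively, so incomplete returns are possible.

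Two stronger readings are tempting. A reader might infer that the threshold in force is 80/1.095 = 73% for the whole per-protocol population. It is not: for completers C_LCV is valid to Visit 15 and the only zero days are non-allowed breaks, which are usually penalised more heavily than a cap would require. A reader might also infer that the per-protocol estimate is pulled towards no effect. The documents do not support that: the subjects concerned are mostly endpoint subjects, and the effect on the hazard ratio depends on their split by arm, which is unknown.

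**Conclusion.** The point holds as a gap in the compliance formula with limited reach. As written, C_LCV can exceed 100%, the excess offsets zero-compliance days, and a subject can be classed as per-protocol who would fail at a true maximum of 100%. At nominal visit spacing with nothing returned, the share of zero-compliance days that passes rises from 20% to about 27%. It can rise further with an early visit, or with an allowed break whose tablets are not returned.

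This rests on surplus tablets being neither returned nor part of a package recorded as lost. The timing limit of about month 24 assumes no clinic visit during the off-drug gap. The number of subjects affected cannot be derived from the documents and is probably small. The primary analysis and secondary endpoints 1–5 use the full analysis population and are unaffected. This is a minor correction, worth making because it is nearly free.

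**What to change.** In SAP 4.8.2 and 6.2.2, state that the pooled C_LCV is truncated at 100% before it enters the overall compliance formula. SAP 5.2 assigns population membership before the blind is broken, so the rule should be set before that step. Report by arm how many subjects had an untruncated C_LCV above 100%.

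The cap should be on the pooled ratio, not on each dispensing interval. Pooling absorbs tablets returned a visit late. A perfect taker who brings nothing to Visit 5 and returns 34 tablets at Visit 7 scores (400 − 34)/366 = 100% pooled. With per-interval capping the score is the mean of 100% and 166/183 = 90.7%, or 95.4%. SAP 8.3 describes compliance as an average of visit-specific measurements, and that sentence should be aligned with the pooled definition. The supply statements in the SAP (200 days) and protocol 10.7.3 (six months plus one week) should be reconciled.

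The cost is one sentence and one line of code. The downside is that a few borderline subjects, mostly with endpoint events, leave PP3 or PP5. These exclusions are related to outcome, which is a further reason to fix the rule under blind and report the counts by arm.

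### The compliance score that decides PP3 and PP5 membership counts a non-allowed treatment break twice when it falls before the last clinic visit

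*SAP*

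**What the plan says.** SAP 4.8.2 builds compliance in two steps.

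- **Step 1, compliance to the last clinic visit (C_LCV).** Pills dispensed minus pills returned are divided by "TD until the final clinic visit - number of days on allowed break before the final clinic visit". SAP 6.2.2 fixes the first term of that denominator: "The number of treatment days until the last clinic visit will be calculated as days from the date of randomization" to the last clinic visit. It is therefore a count of calendar days. Only allowed breaks are subtracted from it, and 4.8.2 describes these as "breaks that are maximum 30 days or related to adjuvant chemotherapy, i.e. breaks that are allowed by the study protocol".
- **Step 2, overall compliance (OC).** OC is a weighted average of C_LCV, over the valid days, and zero, over the zero-compliance days. Under both 4.8.2 and 6.2.2, non-allowed break days are taken out of the valid days. The zero-compliance days are then formed by "adding the number of days on non-allowed treatment break".

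SAP 6.2.2 states which breaks are not allowed: "Treatment breaks that are longer than 30 days and unrelated to adjuvant chemotherapy will be defined as non-compliant with the study protocol".

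SAP 5.2.2 makes compliance of at least 80% a condition for PP3 and PP5. SAP 8.3 makes the analyses on these populations exploratory.

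On the source of the 30-day rule, SAP 4.8.2 gives a general permission: "Subjects are also allowed to pause taking the IMP for up to 30 days in a row during the trial". Protocol 10.7.8 gives its 30-day limit for procedures that need low molecular weight heparin, and separately permits a pause for low platelets during adjuvant chemotherapy. SAP 4.1 also ties the 30 days to surgery.

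**The concern.** Step 1 already charges the subject for a non-allowed break: no pills are taken on those days, yet they remain in the denominator. Step 2 charges the same days again. C_LCV is computed on a set of days that includes the break, and is then applied as the rate for a set that excludes it.

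SAP 4.8.2 says that these days have zero compliance, and SAP 8.3 describes compliance as a weighted average over the whole study period. Under either description, a day off drug should score zero once.

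What is at stake is who enters PP3 and PP5. For subjects with a long non-allowed break, the stated 80% limit becomes a stricter limit that the SAP does not state. Two subjects with the same intake can be classified differently, depending on whether the missed doses were scattered or fell in one break.

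**Working it through.** The SAP gives no worked example, so there is no plan figure to reproduce. The check evaluates its formulas directly.

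**Inputs**
- T: days from randomization to the last clinic visit (6.2.2). For a completer, the date to which C_LCV is valid is Visit 15 (4.8.2), so both periods are T. I take T = 1095 for 3 years. A second case uses T = 365, with the event date equal to the visit date.
- b: non-allowed break days before the last clinic visit, each break longer than 30 days and unrelated to chemotherapy.
- k: share of pills taken on days outside the break. This is an assumption; I use 1.00, 0.95 and 0.90.
- Limit: 80% (5.2.2).

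**Formulas**
- Pills taken = k(T-b), so true intake = k(T-b)/T.
- SAP step 1: C_LCV = k(T-b)/T, because b stays in the denominator.
- SAP step 2: valid days = T-b and zero days = b, so OC = [(T-b)/T] × C_LCV = k((T-b)/T)^2.
- OC falls below 80% when b > T(1 - √(0.8/k)). True intake is at least 80% when b ≤ T(1 - 0.8/k).

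**Example.** With T = 1095, k = 1 and b = 120, true intake is 975/1095 = 89.0%. The SAP gives 0.890^2 = 79.3%, which fails.

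**Windows in which the SAP score fails although true intake is at least 80%**

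| T | k | Bounds on b | Break days | True / SAP, shortest | True / SAP, longest |
|---|---|---|---|---|---|
| 1095 | 1.00 | 115.6 and 219 | 116–219 | 89.4% / 79.9% | 80.0% / 64.0% |
| 1095 | 0.95 | 90.2 and 172.9 | 91–172 | 87.1% / 79.9% | 80.1% / 67.5% |
| 1095 | 0.90 | 62.6 and 121.7 | 63–121 | 84.8% / 79.9% | 80.1% / 71.2% |
| 365 | 1.00 | 38.5 and 73 | 39–73 | 89.3% / 79.8% | 80.0% / 64.0% |

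**Implied score of a break day.** Let v be the score that each break day would need in a single weighted average to reproduce the SAP's OC. Setting [k(T-b) + bv]/T = k((T-b)/T)^2 gives v = -k(T-b)/T. In the 120-day example v = -0.89. The SAP says zero; its formula acts as if the score were negative.

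**Allowed breaks, for comparison.** With a allowed break days, C_LCV = k(T-a)/(T-a) = k and valid days = T, so OC = k. Allowed days are credited at the off-break rate. One 30-day break outside the protocol's stated reasons would change the 80% test only for k from 80% to just under 0.8 × 1095/1065 = 82.25% (T = 1095), or 0.8 × 365/335 = 87.16% (T = 365).

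**The case against.** The strongest reply is that these subjects do not belong in a per-protocol set anyway. Protocol 10.7.8 caps its procedure-related pause at 30 days and SAP 6.2.2 calls longer non-chemotherapy breaks non-compliant, so a subject off drug for 116 days or more is outside the rule. Part of this stands: the sponsor may reasonably want such subjects out. But the formula does not implement that rule, because an otherwise perfect completer with a break of 31 to 115 days still passes. The violation list in 5.2.2 is open-ended but does not name breaks. Its item on lack of compliance stands among reasons for leaving the trial and matches an end-of-study reason in 4.8. If every long break excluded a subject, there would be no purpose in weighting breaks inside OC.

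Nor does the second penalty read as deliberate caution. Where the SAP chooses caution, it says so: 6.2.2 explains that lost packages are counted as unused so that compliance is not overestimated.

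The reply on reach stands in full. SAP Table 9 places the primary endpoint and secondary endpoints 1 to 5 on the FAP. Under 8.3 the per-protocol analyses may or may not be run, carry no p-values, and must be presented with their limitations.

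A reader might infer three stronger things that the documents do not support.

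- *The double count is why shorter breaks exclude subjects with early events.* Any percentage rule does this. Otherwise perfect subjects at 365 and 1095 days first fail at 39 and 116 break days under the SAP, and at 74 and 220 when days are counted once. The ratio is about 1:3 either way.
- *Everyone with 80–89% intake is excluded.* That range needs perfect intake outside the break. At k = 0.95 it is about 80–87%, and at k = 0.90 about 80–85%. A subject at 85% from scattered missed pills is scored correctly.
- *Short breaks must be reclassified by cause.* SAP 4.8.2 states its 30-day rule openly, and the protocol does not expressly forbid other short pauses. Only the attribution to the protocol is inaccurate.

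**Conclusion.** The double count holds as a formula error of minor severity. It applies to breaks of more than 30 days, unrelated to chemotherapy, that fall before the last clinic visit in subjects with pill counts. A break after that visit is counted once. Subjects scored only from the first phone contact have no pill count, so the error does not arise for them.

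For an otherwise perfect subject with such a break, the 80% limit acts as one of about 89%. The windows rest on assumed constant off-break intake and on the last clinic visit coinciding with the end of the valid period.

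The documents give no data on actual breaks, so the number of subjects affected is unknown and may be zero. The same formula applies to both arms, and SAP 5.2 fixes membership before the blind is broken. Nothing here shows a direction or size of bias in a hazard ratio. The primary and secondary efficacy analyses are untouched.

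The attribution of the 30-day rule to the protocol is a secondary wording point: the SAP accepts more than protocol 10.7.8 and its own section 4.1 describe.

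**What to change.** 1. In SAP 4.8.2 and 6.2.2, subtract all break days up to the last clinic visit, allowed or not, from the C_LCV denominator. Keep non-allowed break days as zero-compliance days in OC. Then C_LCV = k and OC = k(T-b)/T, which is the true intake.
2. Decide whether a long non-allowed break should exclude a subject by itself. If so, name it, with a length, among the significant protocol violations in 5.2.2.
3. In 4.8.2, replace the clause attributing the rule to the protocol with a statement that the SAP accepts any break of 30 days or less, or related to adjuvant chemotherapy, and that this is broader than protocol 10.7.8 and SAP 4.1. Align the matching sentence in 6.2.2, which reads "breaks that are at most 30 days of related to chemotherapy will be defined as compliant with the study protocol". The classification itself can stay.

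The changes belong before the blind is broken, when membership is assigned. The cost is one changed denominator and short text edits. Break start and end dates are already in the eCRF (4.8.2), so no new data are needed. The downside is that some subjects with a long non-allowed break may return to PP3 or PP5; step 2 deals with that if it is not wanted.

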5.2.2 Per protocol populations

The per protocol population at 3 years (PP3) consists of all subjects in the FAP who had at least 80 % compliance, fulfill all eligibility criteria, no significant protocol violations, and have either reached a study endpoint (recurrence, other cancer, or death) within 3 years, or completed at least 3 years in the trial.

The per protocol population at 5 years (PP5) consists of all subjects in the FAP who had at least 80 % compliance, no significant protocol violations, fulfill all eligibility criteria, and have either reached a study endpoint (recurrence, other cancer, or death) within 5 years, or completed at least 5 years in the trial.

Subjects who are thought to fulfil all eligibility criteria at randomization, but later are found not to fulfil all eligibility criteria will be excluded from the PP3 and PP5, for example subjects where Lynch syndrome is discovered after randomization.

Significant protocol violations include more than 12 weeks from surgery until randomization, leaving the study because of pregnancy, lack of compliance with the study protocol, wanting to leave the study, refusal to cooperate, other medical reasons, e.g. initiating another treatment not compatible with ASA, or leaving the trial because of an SAE/AE.

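### SAP 4.8.2 sets no 3-year limit on zero-compliance days before an event, while 6.2.2 does; read literally, 4.8.2 removes fully compliant subjects with late events from PP5

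*SAP*

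**What the plan says.** On treatment length, SAP 4.8 states: "The treatment period begins at the randomization visit and ends after 3 years". It adds: "Subjects leave the IMP part of the trial at Visit 15, or at fulfillment of an end of study (EoS) reason".

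SAP 4.8.2 defines overall compliance (OC) as a weighted average of measured compliance over valid days and 0% over zero-compliance days. Valid days run from randomization to a date D. The rules are:

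- **Recurrence, death or other cancer:** D "will be defined as the date of last IMP intake, if such a date is registered in the eCRF, or the event date", whichever is earlier. Days from D "until the event date will be defined as having 0 % compliance".
- **Completing 3 years:** D is the Visit 15 date. No later zero-compliance days are described.
- **Leaving early without an endpoint:** days from D "until 3 years from randomization will be defined as having 0 % compliance".

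SAP 6.2.2, which derives the variables, ends the zero-compliance days at the recorded end-of-study date "or 3 years from randomization, adding the number of days on non-allowed treatment break". It also refers back to 4.8.2 for the definition of overall compliance.

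SAP 5.2.2 requires at least 80% compliance for PP5, and that subjects "have either reached a study endpoint (recurrence, other cancer, or death) within 5 years, or completed at least 5 years in the trial". SAP 8.3, Table 11, uses PP5 for exploratory 5-year TTR and OS in Mutation A, Mutation B and both combined.

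**The concern.** Compliance should describe how a subject took the tablets while tablets were due. In 4.8.2 the early leavers' count stops at 3 years, but the count for subjects with an endpoint runs to the event. PP5 accepts endpoints up to 5 years, so the event can lie well beyond the last planned tablet. Days on which no tablet was due would then count as missed treatment, but only for subjects who later had an event.

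If that rule is applied, PP5 membership depends on the outcome. Among completers with identical intake, those with a late event go and those without one stay at risk to year 5. Late event rates would be understated in both arms. The stabilized weights in 8.3 use baseline covariates to model treatment received, so they cannot correct for selection on a later event.

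Timing adds to the risk. SAP 5.2 wants population status assigned before the blind is broken. SAP 5.1 plans the 3-year comparison soon after August 9, 2024, and the 5-year OS analysis from August 19, 2026. For subjects randomized late, PP5 status cannot be known until after the 3-year arms have been compared. A choice between readings left open until then would be made with those results in hand.

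**Working it through.** The plan gives no figure for this point, so there is none to reproduce.

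**Inputs.** Treatment length 3 years (SAP 4.8); threshold 80% (5.2.2); Visit 15 window ±21 days and Visit 16 window ±30 days (4.8, Table 4); OC formula (4.8.2). C is compliance to the last clinic visit and t is event time in years, with t > 3.

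**Step 1: literal 4.8.2 with D at year 3** (Visit 15, or a registered last intake near it). Valid days are 3 years and zero-compliance days are t − 3 years:

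OC = [3 × C + (t − 3) × 0] / [3 + (t − 3)] = 3C/t.

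**Step 2: the other two readings.** With no registered last intake, the event rule in 4.8.2 makes D the event date. There are then no zero-compliance days and OC = C. Under 6.2.2 the zero-compliance days stop at the end-of-study date or 3 years, so OC = C again. This last result assumes that a completer's end-of-study date is about Visit 15.

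| Event time (years), C = 100% | OC, literal 4.8.2, D = 3 years | OC, 6.2.2 or D = event date |
|---|---|---|
| 3.25 | 92.3% | 100% |
| 3.5 | 85.7% | 100% |
| 3.75 | 80.0% | 100% |
| 4 | 75.0% | 100% |
| 4.5 | 66.7% | 100% |
| 5 | 60.0% | 100% |

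An event-free completer has OC = C throughout.

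**Step 3: cut-off under the literal reading.** OC < 0.80 when t > 3C/0.80:

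- C = 100%: 3.75 years (3.68 to 3.82 if Visit 15 is 21 days early or late)
- C = 95%: 3.56 years
- C = 90%: 3.38 years
- C = 85%: 3.19 years

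At C = 100% the excluded part of the period from year 3 to 5 years plus 30 days is (5.082 − 3.75) / (5.082 − 3) = 64%.

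**Step 4: share of events exposed.** The documents give no 5-year event risk R, so I assume 10% to 20% and a constant hazard. Then S(t) = (1 − R)^(t/5), and the share of 5-year first events after cut-off t* is [S(t*) − (1 − R)] / R. Example for R = 20% and t* = 3.75: (0.845897 − 0.80) / 0.20 = 22.9%.

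| 5-year risk | after 3.75 y (C = 100%) | after 3.56 y (C = 95%) | after 3.38 y (C = 90%) |
|---|---|---|---|
| 20% | 22.9% | 26.5% | 30.1% |
| 10% | 24.0% | 27.7% | 31.4% |

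**Step 5: PP3.** The latest 3-year event is at 3 years plus 21 days and the earliest in-window Visit 15 at 3 years minus 21 days. With 3 years = 1095.75 days, OC = 1074.75 / 1116.75 = 96.2% at full intake, so the literal rule barely touches PP3.

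**The case against.** The strongest reply is that the SAP already contains the limit. Section 4.8.2 sends the programmer to 6.2.2, and 6.2.2 names 3 years from randomization. Completers leave the IMP part at Visit 15, and 6.2.1 lists a death date entered at Visit 16 separately from the end-of-study date. On that footing the 4.5-year example has 100% compliance and stays in PP5. Moreover, 6.2.2 takes the event date from a DFS variable, and 6.2.1 defines DFS only to 3 years plus 21 days. That points to a rule written for 3-year events. Finally, the event rule does not mention Visit 15: where no last intake is registered, D is the event date and no zero-compliance days arise.

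Much of this stands. A reader might infer that the SAP excludes everyone with a late event, or that PP5 will contain no events after 3.75 years. The documents do not support either: exclusion follows under one of three readings, and the cut-off concerns the first event, so a death after an earlier recurrence could still count for OS. Nor do they support a claim that the hazard ratio is biased in a known direction, because the rule is the same in both arms.

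The reply does not settle the matter, however. Section 6.2.2 refers back to 4.8.2 for the definition, and that definition has no limit. The end-of-study date for completers is inferred, not stated. The 3-year DFS date does not fit a PP5 population that counts endpoints to 5 years. For a completer with a late event, 4.8.2 supports both Visit 15 and the event rule as the source of D, so membership could turn on whether a last-intake date happens to be in the eCRF.

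**Conclusion.** The two sections conflict, and the D rules within 4.8.2 overlap, for 3-year completers with a later event. One reading selects on outcome: a fully compliant completer is lost from PP5 when the event comes after 3.75 years, and earlier with less complete intake. The other two readings drop nobody for this reason.

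Under the literal reading, about 23-31% of first events within 5 years fall after the cut-offs. That figure rests on the assumed constant hazard, the assumed 10-20% five-year risk and on-treatment compliance of 90-100%. The size and direction of any effect on the hazard ratio cannot be computed from the documents.

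The reach is limited. The primary endpoint and secondary endpoints 1-5 use the full analysis population and are unaffected. The PP5 analyses in Table 11 are exploratory, optional and reported without p-values. PP3 would be exposed to the late-event cut-off only if the single indicator overall_compl_80 were recalculated with late events and then reused for PP3. The wording should still be settled, because the correction is small and the alternative is a PP5 population that may depend on outcome.

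**What to change.** In 4.8.2, and in the same words in 6.2.2:

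- For subjects with an endpoint, end both valid days and zero-compliance days no later than the earlier of the event date and the planned end of treatment: Visit 15, or 3 years from randomization if there is no Visit 15.
- State that D is Visit 15 for subjects who complete 3 years, even if an event follows.

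Compliance then covers only days on which tablets were due, for subjects with and without events alike. A fully compliant completer has OC = 100% whatever happens in years 3 to 5.

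Do not reconcile the sections by extending 6.2.2 to an event date without a limit. That would remove the inconsistency and make the outcome-dependent exclusion the rule.

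The cost is one clause in each section and a minimum of two dates in the code. No new data are needed. Under SAP 5.1, 5-year follow-up including the visit window is not complete until August 2026, so the text can be settled before PP5 is assigned.
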